7.3 Immunogenicity Endpoint Summaries

Participants with evidence of SARS-CoV-2 infection or that received an off-study vaccine will be censored from the immunogenicity analysis for all timepoints and evaluations beyond earlier of the time point at which evidence of SARS-CoV-2 infection occurred or the time point at which off-study vaccine was received. Evidence of SARS-CoV-2 infection includes a positive PCR test or a positive antinucleocapsid antibody test (defined as a concentration $\geq 5,000$ AU/ml)

The timepoints for analysis of each of the immunogenicity parameters is shown in Appendix 9.1.

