- For participants in Cohort 2, immunogenicity data from the Parent Study for tests using the same assays as being performed in ARCT-021-02 is available only for participants in Cohorts 2 (D1), 2 (D2), 2 (E) and 2 (G). For these participants the Parent Study data will be presented together with the data from Day 29 in Study ARCT-021-2 (Day 29 is the only time point for which data is available for these cohorts in ARCT-021-02). For the remaining participants in Cohort 2 only data from Day 29 in Study ARCT-021-02 will be presented, as this is the only data (from the relevant assays) available at the time of this interim.

Table 2: Immunogenicity Data to be Included in Interim Analysis #1

Study/Time Point	Cohort/Sub-Cohort								
	1a	1b (A/C)	1b (B)	1b(D1/D2)	2 (A/C)	2 (B)	2 (D1/D2)	2 (E/G)	2 (F/H)
Parent Study									
Day 1	NA	NA	NA	X	NA	NA	X	X	X
Day 29	NA	NA	NA	X	NA	X	X	NA	X
Day 43	NA	NA	NA	X	NA	NA	X	X	X
Day 57	NA	NA	X	X	NA	NA	X	X	X
Day 85	NA	NA	NA	NA	NA	NA	NA	X	X
ARCT-021-02									
Day 1	X	X	X	X	NA	NA	NA	NA	NA
Day 29	X	X	X	X	X	X	X	X	X
Day 57	X	X	X	X	NA	NA	NA	NA	NA

NA = Not available/not applicable

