5.3.1 Baseline

For Safety Analysis, the following conventions will be applied for the definition of baseline:

For the Safety Population baseline will be the last value prior to first administration of ARCT-021 in Study ARCT-021-02.

For the Longitudinal Safety Population baseline will be the last value prior to first administration of ARCT-021 in either the ARCT-021-01 or ARCT-021-02 study (whichever study represented the first ARCT-021 vaccination)

For the Immunogenicity Analysis, Immunogenicity baseline will be defined as:

- Cohort 1a and 1b: Last value prior to or on Day 1 of ARCT-021-02
- Cohorts 2 (A to D2) and 2 (E to H): Last value prior to or on Day 1 of ARCT-021-01

For assessments collected during the screening period as well as on Day 1, the Day 1 value will be used as baseline. If more than one assessment exists within a single visit window, the value closest to the protocol study visit will be used for summary and analysis purposes. If more than one equidistant to the protocol study visit assessments exists, then earliest of these values will be used for summary and analysis purposes. Data from all assessments will be listed.

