5.3.2 Study Day in Study ARCT-021-02

For Adverse events, Study day will be determined based on actual number of days since study Day 1. Study Day 1 will be identified from the CRF. For Cohort 1, it will be the day of vaccination. Study day for any given date will be:

- Given Date – Study Day 1 + 1 for dates on or after date of Study Day 1.
- Given Date – Study Day 1 for dates before date of Study Day 1.

For all immunogenicity data, the Study Day will be based on the nominal study day as captured in the CRF. For participants that received their first dose of ARCT-021 in the Parent study, nominal day since Day 1 in the Parent Study will also be displayed, as follows:

- For cohorts 1b (A to D2) and 2 (A to D2) Day 1 in Study ARCT-021-02 = Day 147 after Day 1 in the Parent Study, calculated as follows:
 - The time enrolled in the Parent Study is 57 days and the time between Parent Study and Day 1 in Study ARCT-021-02 is nominally 90 Days. Therefore, Day 1 in Study ARCT-021-02 is $57 + 90 = 147$ days after Day 1 in the Parent Study
- For cohorts 2 (E to H) Day 1 in Study ARCT-021-02 = Day 175 after Day 1 in the Parent Study, calculated as follows:
 - The time enrolled in the Parent Study is 85 days and the time between Parent Study and Day 1 in Study ARCT-021-02 is nominally 90 Days. Therefore, Day 1 in Study ARCT-021-02 is $85 + 90 = 175$ days after Day 1 in the Parent Study

Based on the above, in the Immunogenicity tables the visit name (when they are shown) will be displayed showing the nominal day from parent study within parenthesis. The nominal days will depend on the cohort and they will be as follows:

Table 3: Label for reporting Visit Days in safety and immunogenicity when needed.

Visit name in Protocol	Cohort			
	1a	1b	2 (A-D2)	2(E-H)
Day 1	Day 1	Day 1 (147)	Day 1 (147)	Day 1 (175)
Day 29	Day 29	Day 29 (175)	Day 29 (175)	Day 29 (203)
Day 43	Day 43	Day 43 (189)	Day 43 (189)	Day 43 (217)
Day 57	Day 57	Day 57 (203)	Day 57 (203)	Day 57 (231)
Day 85	Day 85	Day 85 (231)	Day 85 (231)	Day 85 (259)

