5.4 Handling of Dropouts or Missing Data

Due to the exploratory nature of this study and the lack of statistical testing, missing data will not be imputed. Values that are below the level of quantification will be recoded to zero for analysis purposes, with the exception of antibody titers which will be recoded to LLOQ/2.

For participants who received an off-study vaccine, Safety and Immunogenicity reports will be censored at date of first dose of off-study vaccine. Safety data after off-Study vaccine will be reported separately.

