7.2 Secondary Immunogenicity Endpoints and Analyses

As per scheduled assessment, Cohort 1 will be reported at Study Day 29, Study Day 57, Study Day 169 and Study Day 365/Early termination, however only immunogenicity data up to ARCT-021-02 Day 57 will be available at the time of this interim. Cohort 2 will be reported at Study Day 29 (6 months FU), Study Day 197(12 Months FU) and Study Day 281 (15 Month FU)/Early Termination, however only immunogenicity data up to ARCT-021-02 Day 29 will be available at the time of this interim.

1. Mean and geometric mean titer or concentration (GMT, GMC) and the geometric mean fold rise (GMFR) in SARS-CoV- 2 neutralising antibody titer and IgG antibodies against the full-length SARS-CoV-2 recombinant spike protein antigen, RBD and N-antigen at multiple time points in each cohort.

Assessment of the long-term neutralising and anti-spike glycoprotein responses, including seroconversion rates, following vaccination with ARCT-021 is the secondary objective of the study. The study endpoint for these analyses include:

Assays:

- Neutralising antibody responses: pseudovirus neutralization test

- Binding antibody responses: Total IgG against the full-length SARS-CoV-2 recombinant spike protein, RBD and N-antigen will be assessed using a Meso-Scale Discovery (MSD) multiplex technology.

Endpoints at this interim:

- Cohort 1: Neutralising and binding antibody responses at Day 1, Day 29 (1 month after last dose of ARCT-021), Day 57 (2 months after last dose of ARCT-021)
- Cohort 2: Neutralising and binding antibody responses at ARCT-021-02 Day 29 (6 months after last dose of ARCT-021), which is Day 176 for Cohort 2 (A to D2) and Day 204 for Cohort 2 (E to H)

Descriptive statistics, by assessment time point, will be used to describe all immunogenicity results.

Mean and geometric mean titer (GMT) and geometric mean fold rise (GMFR) will be calculated for each cohort/sub-cohort (Section 5.2) in the Immunogenicity analysis population. The %GCV, median, standard deviation, minimum, and maximum values will also be displayed.

The GMT will be calculated as:

$$\text{GMT} = \text{anti-log}_{10} (\text{mean} [\log_{10} Y_i])$$

The GMFR will be calculated as:

$$\text{GMFR} = \text{anti-log}_{10} (\text{mean} [\log_{10} Y_i / B_i])$$

where Y_i is the post dose assay result for participant i ; and B_i is the baseline assay result for participant i . The exact 95% CIs will be provided for both GMT and GMFR.

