7.3.1.1 Binding Antibodies

Endpoint titers of Binding antibodies, by participant, and time point, will be listed for each of the 3 tests listed below. Mean titer, GMC, GMFR, 95% CIs, median, minimum, and maximum values and number and percent of participants seroconverting will also be summarized by cohort/sub-cohort and time point for:

- Anti-spike glycoprotein
- Anti-RBD
- Nucleocapsid

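### The infection-censoring rule in SAP 7.3 keeps the visit at which anti-nucleocapsid antibody first turns positive, so infection-boosted spike, RBD and neutralising results can enter the summaries

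*SAP*

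**What the plan says.** SAP 7.3 removes participants with evidence of infection, or with an off-study vaccine, from the immunogenicity analysis "for all timepoints and evaluations beyond earlier of the time point at which evidence of SARS-CoV-2 infection occurred" or the off-study vaccine was received. Evidence of infection includes "a positive PCR test or a positive antinucleocapsid antibody test", the latter set at 5,000 AU/ml or more.

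The serological evidence comes from the assay that supplies the binding-antibody endpoints. SAP 7.2 states: "Total IgG against the full-length SARS-CoV-2 recombinant spike protein, RBD and N-antigen will be assessed using a Meso-Scale Discovery (MSD) multiplex technology". Neutralising antibody is reported at the same visits. SAP 7.3.1.1 adds that the "number and percent of participants seroconverting will also be summarized by cohort/sub-cohort and time point for" anti-spike, anti-RBD and nucleocapsid.

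Few visits are available at this interim. Under SAP 4.4, Cohort 1 has ARCT-021-02 Days 1, 29 and 57. For the Cohort 2 groups with Parent Study data, "Day 29 is the only time point for which data is available for these cohorts in ARCT-021-02", and the remaining Cohort 2 participants contribute Day 29 alone.

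For off-study vaccine the SAP has further text. SAP 5.4 says "Safety and Immunogenicity reports will be censored at date of first dose of off-study vaccine", and SAP 3.1 and 5.3.3 are similar. None of these sections deals with infection.

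**The concern.** The word *beyond* suits an off-study vaccine, because a sample taken on the day of vaccination does not yet reflect it. It does not suit serology, which lags infection. Protocol 2.5.1 describes the construct as a replicase gene plus the spike sequence, so the vaccine is not expected to raise anti-N. A positive anti-N draw therefore points to an infection that came first. The rule marks the visit as infection-affected and then keeps its spike, RBD and neutralising values.

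Detection by serology first is foreseeable. Protocol 2.1 says infection is asymptomatic in many cases, and Protocol 6.2.4 triggers PCR by symptoms or known exposure. In Protocol Appendix 1, participants not dosed in this study have no immunogenicity test scheduled at ARCT-021-02 Day 1. Where a screening immunogenicity sample is taken, it is PRNT50 only.

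Long-term antibody response is the secondary objective, and SAP 4 says this interim supports a regulatory filing. An undetected infection that lifts the Cohort 2 Day 29 value would look like durability of the vaccine response.

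**Working it through.** The plan gives no figure on this point to reproduce. The check applies the rule to the interim visits and then illustrates the effect of one retained value.

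**1. Visits kept when the first evidence is an anti-N-positive sample.** As written, visit t is kept if t ≤ the evidence visit. Under an *at and after* rule it is kept only if t < the evidence visit. ARCT-021-02 visits are from SAP 4.4.

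| Cohort | First anti-N positive | Kept as written | Kept under *at and after* |
|---|---|---|---|
| 1 | Day 1 | Day 1 | none |
| 1 | Day 29 | Days 1, 29 | Day 1 |
| 1 | Day 57 | Days 1, 29, 57 | Days 1, 29 |
| 2 | Day 29 | Day 29 | none |

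At all three post-baseline visits the first-positive sample is retained. At two of them (Cohort 1 Day 57, Cohort 2 Day 29) no later interim visit exists, so nothing is censored. A Cohort 1 Day 1 positive does no harm to fold rise or seroconversion, because Days 29 and 57 are already removed.

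**2. Time in which an infection could go undetected (Cohort 2).** SAP 5.3.2 says "the time between Parent Study and Day 1 in Study ARCT-021-02 is nominally 90 Days". For 2(D1/D2) and 2(E to H), the last Parent Study visits are Days 57 and 85.

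- With the Table 3 labels: 175 − 57 = 118 days and 203 − 85 = 118 days.
- With the day numbers in SAP 7.2: 176 − 57 = 119 days and 204 − 85 = 119 days.

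**3. Which summaries are exposed.** The geometric mean titre or concentration (GMT/GMC) is exposed in any sub-cohort. Geometric mean fold rise and seroconversion are exposed only where a baseline exists. Cohort 1 uses ARCT-021-02 Day 1. For the rest, SAP 5.3.1 sets "Cohorts 2 (A to D2) and 2 (E to H): Last value prior to or on Day 1 of ARCT-021-01". In SAP Table 2, 2(A), 2(B) and 2(C) have no Parent Study Day 1 value, so those two summaries are unaffected there. Table 2 marks 2(F/H) as having one, but the text of SAP 4.4 limits same-assay Parent Study data to 2(D1), 2(D2), 2(E) and 2(G). Exposure of 2(F) and 2(H) is therefore unresolved.

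**4. Illustrative size.** If one of n participants has a titre f times what it would have been without infection, log GMT shifts by (log f)/n, so the GMT is multiplied by f^(1/n). If that participant would not otherwise have seroconverted, the rate rises by 100/n percentage points; if they would have, it does not change.

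| n | f = 5 | f = 10 | f = 30 | Seroconversion, at most |
|---|---|---|---|---|
| 7 | 1.26 | 1.39 | 1.63 | +14.3 points |
| 20 | 1.08 | 1.12 | 1.19 | +5.0 points |
| 40 | 1.04 | 1.06 | 1.09 | +2.5 points |

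Both n and f are assumptions. The value n = 7 is 106/15 ≈ 7.1: the 106 participants in SAP 3.1 spread equally over the 15 sub-cohorts in SAP 5.2 (one 1a, five 1b, nine in Cohort 2).

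**The case against.** - **The sponsor may have meant *at or beyond*.** This is possible, and the off-study-vaccine text in SAP 5.4 points that way. But no section states it for infection, and *evaluable* in the SAP 5.2 population definition is not defined.
- **The case would be visible.** Protocol 9.3.7 makes an anti-N positive in an asymptomatic participant a clinical event of special interest (CESI) if they were negative before entry. SAP 8.1.8 requires a listing and narrative, and SAP 7.3.1.1 and 7.3.1.2 list antibody results by participant. This is true, but a listing does not correct a geometric mean.
- **Surveillance narrows the gap.** Participants are questioned at every visit, exposure prompts PCR, CESIs since the Parent Study are solicited at screening, and retained serum can be tested for anti-N (Protocol Appendix 2). Any earlier positive removes the later visit. In Cohort 1, after a negative previous sample, infection and anti-N conversion must fall within a nominal 28 days. This limits frequency and makes Cohort 2 the likelier place for the problem; it does not close the gap.
- **A false-positive anti-N result would delete valid data.** The documents give no specificity for the cut-off. The SAP accepted that risk when it made this threshold evidence of infection.
- **The analysis is descriptive and the size is assumed.** Both points stand. They limit the urgency, but the direction of the expected bias is clear.

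**Conclusion.** The rule is wrong as written and should be fixed. When serology is the first evidence of infection, SAP 7.3 retains spike, RBD and neutralising results that can include the infection response, and at two of the three post-baseline ARCT-021-02 visits it censors nothing at this interim. The expected bias is upward in GMT/GMC, and in fold rise and seroconversion where a baseline exists.

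Confidence in this reading is high. The actual effect is unknown, because the documents give no infection counts, sub-cohort sizes or boost, and it is zero if no participant is detected by serology first. On the assumed values, one case could matter in a sub-cohort of about 7 and would be modest in one of 40.

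**What to change.** In SAP 7.3, for the spike, RBD and neutralising antibody summaries, state that results are excluded at and after the first sample with anti-N of at least 5,000 AU/ml, or from the date of the first positive PCR if that is earlier.

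Present the nucleocapsid summaries in SAP 7.3.1.1 without this infection censoring. Otherwise every positive sample would drop out of them by construction. The nucleocapsid tables will then have different denominators from the spike and RBD tables, which a footnote can explain. No separate baseline exclusion is needed for fold rise or seroconversion. A sensitivity analysis that keeps the first-positive visit would show how much the choice matters.

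The cost is one sentence, one exception and one programming flag, with slightly fewer observations in small sub-cohorts. SAP 5.1 bars changes to this interim SAP once the data are pulled. If that has happened, put the rule in the final-analysis SAP and report the *at and after* version of the interim tables as a disclosed sensitivity analysis.

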7.3.1 Antibody Responses

All antibody responses will be shown by specified Cohort and Sub-Cohort described in Section 5.2.

7.3.1.1 Binding Antibodies

Endpoint titers of Binding antibodies, by participant, and time point, will be listed for each of the 3 tests listed below. Mean titer, GMC, GMFR, 95% CIs, median, minimum, and maximum values and number and percent of participants seroconverting will also be summarized by cohort/sub-cohort and time point for:

- Anti-spike glycoprotein
- Anti-RBD
- Nucleocapsid

7.3.1.2 Neutralizing Antibodies

Levels of SARS-CoV-2 neutralizing antibodies by participant, cohort and time point will be listed. Mean titer, GMT, GMFR, 95% CIs, median, minimum, and maximum values and number and percent of participants seroconverting will also be summarized by cohort/sub-cohort and time point.

8. SAFETY ANALYSIS

The primary objective of the study is the evaluation of the safety of ARCT-021. The primary endpoints that align with this objective are:

- Solicited AEs for 7 days after vaccination with ARCT-021 (Cohort 1 only).
- Unsolicited AEs within 28 days after vaccination with ARCT-021 (Cohort 1 only), summarized by mild/moderate/severe and relationship to ARCT-021.
- SAEs, MAAEs, NOCD and AE leading to discontinuation/withdrawal according to the following windows
 - Pre-Study for cohort 1b
 - Within 28 days after vaccination with ARCT-021 (Cohort 1 only)
 - from 28 days after vaccination to the last observation prior to receipt of off study vaccine or prior the data cut point for this interim, whichever is first (all cohorts/sub-cohorts).
- Safety laboratory assessments through 28 days after vaccination with ARCT-021 (Cohort 1 only), summarized by toxicity grade (where relevant).
- Vital signs assessments through the last observation prior to receipt of off study vaccine or prior to the data cut point for this interim, whichever is first, summarized by toxicity grade.
- Unsolicited AEs, MAAEs, SAEs and vital signs assessments from after receipt of off-study vaccine up to the observation prior to the data cut point for this interim.

8.1 Adverse Events

All AEs will be reported for participants receiving study vaccine in this Study (Cohort 1), up to 28

days after injection. SAEs, CESIs, NOCDs, and MAAEs will be reported for all participants up to the last time point evaluated after injection, i.e., up to the time of the data cut point for this interim.

For participants in Cohorts 1b and 2 (i.e. those that received ARCT-021 in the Parent Study), any MAAE, NOCD or CESI events occurring between the Parent Study and the screening visit for this study were recorded in the eCRF for this study and will be included in the safety data presented.

For participants that received an off-study vaccine, safety data prior to and after the receipt of off-study vaccine will be presented separately.

8.1.1 Treatment-emergent Adverse Events

All adverse events that start on or after study vaccine administration are classified as treatment emergent adverse events (TEAEs).

- For Cohort 1a, treatment emergent events are those arising after receipt of ARCT-021 on Day 1 in Study ARCT-021-02
- For Cohort 1b and Cohort 2, treatment emergent events comprise any events occurring since the participant exited the Parent Study

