9.4 Monitoring and Recording Adverse Events

Any pre-existing conditions or signs and/or symptoms present in a subject prior to the first injection of ARCT-021 should be recorded as Medical History and not recorded as AEs unless the pre-existing condition worsened. The Investigator should always group signs and symptoms into a single term that constitutes a **single unifying diagnosis** if possible. Before a diagnosis is confirmed, all symptoms should be reported as separate AEs.

Any AE that includes a new diagnosis of a chronic medical condition that was not present or suspected prior to enrollment, will be categorized as a new onset of chronic disease (NOCD).

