9.4.3 Non-Serious Adverse Events

For subjects who receive ARCT-021 in this study and who did not receive ARCT-021 in the Parent Study, the recording of non-serious AEs will begin after the subject has received ARCT-021 and will stop 28 days after the last dose of ARCT-021, with the exception of ongoing adverse events that worsen in severity and/or become serious, which will continue to be recorded. AEs that occur prior to administration of ARCT-021, including those that occurred between leaving the Parent Study and dosing in this Study will be recorded as medical history.

For subjects who receive ARCT-021 in this study and who also received ARCT-021 in the Parent Study, the recording of non-serious AEs will begin from the time the subject received ARCT-021 in the Parent Study and will stop 28 days after the dose of ARCT-021 in this study, with the exception of ongoing adverse events that worsen in severity and/or become serious, which will continue to be recorded. Any AEs that occurred between leaving the Parent Study and entering this study will be recorded as AEs.

For subjects who do not receive ARCT-021 in this study, only medically attended non-serious events will be recorded as described above (Section 9.4.2). The Investigator will monitor each subject closely and record all observed or volunteered AEs in the EDC.

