8.1.9.1 Unsolicited Adverse Event Summaries

All unsolicited AEs (serious and non-serious) occurring after exiting Parent study and after administration of first dose of study vaccine (in this study or parent study as applicable) and before the End of Study or Off-study vaccination, regardless of relationship to study vaccine, will be included and classified by system organ class (SOC) and preferred term (PT) using the Medical Dictionary for Regulatory Activities (MedDRA).

- For Cohort 1a, AE occurring from the time of exiting the Parent Study up to receipt of Study Vaccine on Day 1 will be regarded as medical history. All unsolicited events, including SAEs, MAAEs, and NOCD are collected up to 28 days after receipt of study vaccine and only SAEs, MAAEs, and NOCD are collected beyond 28 days after receipt of study vaccine.
- For Cohort 1b, SAEs, MAAEs, and NOCD occurring from the time of exiting the Parent Study up to receipt of study vaccine on Day 1 will be regarded as treatment emergent but will be presented separately (as 'Pre-Study TEAEs') to TEAEs occurring after receipt of vaccine. All unsolicited events, including SAEs, MAAEs, and NOCD are collected up to 28 days after receipt of study vaccine in Study ARCT-021-02 but only SAEs, MAAEs, and NOCD are collected beyond 28 days after receipt of study vaccine.
- For Cohort 2 only SAEs, MAAEs, and NOCD are collected in Study ARCT-021-02 as no further study vaccine is administered in this study. All events reported from the time of exiting the Parent Study up to the data cut point for this interim analysis are regarded as treatment emergent and will be presented merged for the purposes of tabulation.

Solicited systemic and local adverse events will not be included in the unsolicited AE summaries, unless the solicited AE has onset >7 days after administration of Study vaccine or the solicited event is serious or medically attended.

Unsolicited AEs that appear within the Toxicity Grading Scale for Healthy Adult and Adolescent Volunteers Enrolled in Preventive Vaccine Clinical Trials, Sept 2007 will have been entered in the EDC with a numerical Grade (1 to 4). Unsolicited TEAEs that are not contained within this scale will have been graded as mild/moderate/severe. For the purposes of tabulation of unsolicited AEs, events will be presented as mild/moderate/severe, whereby the CRF-designated Grade 1 = mild, Grade 2 = moderate and \geq Grade 3 = severe.

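### SAP 8.1.1 classifies events by start date only, so a Cohort 1b event that begins between studies and worsens or becomes serious after the injection can be shown as pre-dose, depending on how it is entered

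*SAP*

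**What the plan says.** SAP 8.1.1 gives one general rule and two cohort rules. The general rule is "All adverse events that start on or after study vaccine administration are classified as treatment emergent adverse events (TEAEs". For participants first vaccinated in this study, "For Cohort 1a, treatment emergent events are those arising after receipt of ARCT-021 on Day 1 in Study ARCT-021-02". For the rest, "For Cohort 1b and Cohort 2, treatment emergent events comprise any events occurring since the participant exited the Parent Study". No sentence covers an event that is present before the injection and changes after it.

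SAP 8.1.9.1 then splits Cohort 1b at the Day 1 injection. SAEs, MAAEs and NOCDs "occurring from the time of exiting the Parent Study up to receipt of study vaccine on Day 1 will be regarded as treatment emergent", but they go into a Pre-Study display, separately "to TEAEs occurring after receipt of vaccine". SAP 8 lists the Pre-Study period for Cohort 1b and the 28 days after vaccination as different windows under the primary safety endpoints.

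On recording, protocol 9.4 says that conditions present before the first ARCT-021 injection "should be recorded as Medical History and not recorded as AEs unless the pre-existing condition worsened". Protocol 9.4.3 enters between-study events as AEs for participants dosed in both studies. It stops recording of non-serious events 28 days after the dose, "with the exception of ongoing adverse events that worsen in severity and/or become serious, which will continue to be recorded". SAP 5 agrees that pre-Day 1 events are AEs in Cohort 1b and medical history in Cohort 1a. Protocol 6.2.1, in its paragraph on participants given ARCT-021 in the Parent Study, instead sends events before dosing in this study to medical history.

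**The concern.** A safety table for boosted participants should show whether an existing condition gets worse after a further exposure. The protocol treats worsening as reportable: 9.3.1 includes exacerbation of an existing disease in its definition of an adverse event. The SAP does not carry this into its windows.

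Cohort 1b is the group re-dosed in this study (parent Cohorts E to H also had two doses, but both in the Parent Study). If a worsened 1b event is displayed as pre-dose, three things follow:

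- The post-vaccination incidence and severity for 1b are understated.
- The Pre-Study display carries a grade or seriousness that arose after the injection.
- The 1a and 1b columns are not built on the same rule.

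The interim analysis supports a regulatory filing (SAP 4), and SAP 8.1.9.1 specifies these tables for the final analysis.

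**Working it through.** The plan has no figure to reproduce. The check follows one case through the rules: a medically attended event starts between Parent Study exit and Day 1, is ongoing and mild at the injection, and becomes severe or serious afterwards.

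| Route | Pre-dose part entered as | Change entered as | Start date | Display |
|---|---|---|---|---|
| Cohort 1a | Medical history (SAP 5) | New AE (protocol 9.4) | After the injection | Post-vaccination |
| Cohort 1b, same record kept | AE (protocol 9.4.3, SAP 5) | Higher grade or seriousness on that record | Before the injection | Pre-Study |
| Cohort 1b, new record opened | AE (protocol 9.4.3, SAP 5) | New AE (protocol 9.3.1) | After the injection | Post-vaccination |
| Cohort 1b, protocol 6.2.1 followed | Medical history | New AE only if protocol 9.3.1 or 9.4 is applied | After the injection, if entered | Post-vaccination, if entered |

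Four points from the text support the table.

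1. Protocol 9.4 does not settle the Cohort 1b case. It concerns conditions present before the first ARCT-021 injection, which these participants had in the Parent Study.
2. Protocol 9.4 speaks of worsening, not of becoming serious. The Cohort 1a row is firm for an increase in severity. For new seriousness it relies on SAE collection from dosing onward in protocol 9.4.1.
3. Under SAP 8.1.1 a Cohort 1b event is treatment-emergent on either side of Day 1. The question is only which display it enters, and the start date is the one dating rule that the SAP states.
4. Nothing later in the SAP repairs this. The counting rule in 8.1.9.1 picks the worst of repeated episodes and does not address a grade change within one event. The listings in 8.1.4 to 8.1.6 carry onset and resolution dates, with no date of worsening or of becoming serious.

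Size. The documents give total enrolment only (about 99, at most 166, in protocol 3.6; 106 in SAP 3.1). They give no number for Cohort 1b and no rate of ongoing or worsening events. If one participant is misplaced and has no other event in the same table row, the shift in post-vaccination incidence is 100 × 1/n percentage points. With n assumed:

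- n = 10: 100/10 = 10 points
- n = 20: 100/20 = 5 points
- n = 40: 100/40 = 2.5 points

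The summaries are also produced by sub-cohort, where n is smaller and the shift larger.

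**The case against.** A reader might infer that the SAP tabulates every worsened Cohort 1b event as Pre-Study. The documents do not say so. Protocol 9.3.1 lets a worsening be an adverse event in its own right in any cohort, and a new record would start after the injection and be counted. The cohort text in SAP 8.1.1 and 8.1.9.1 speaks of events occurring, and the windows in SAP 8 name no date for assignment. This objection stands, and it makes the misplacement conditional on the record being kept.

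A reader might also take the wording in protocol 9.4.3, "with the exception of ongoing adverse events that worsen in severity and/or become serious, which will continue to be recorded", as an instruction to keep one record. It is an exception to the 28-day stop and is silent on records and onset dates. It also appears in the paragraph on participants first dosed here, so it cannot by itself create a difference between 1a and 1b.

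A percentage built from an assumed share of ongoing events and an assumed chance of worsening would rest on nothing in the documents. The pool is probably small: re-dosed participants must be healthy in the investigator's opinion (protocol 5.1), new clinically significant abnormalities exclude (5.2), and acute illness defers vaccination (8.7.1).

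Finally, each SAE, MAAE and NOCD is listed and has a narrative (SAP 8.1.4 to 8.1.6), and the analysis is descriptive. So the event is not lost and no test is affected. The primary safety counts can still be wrong, and the listings do not show when the change happened.

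**Conclusion.** The concern holds in conditional form. The SAP's stated rule is onset-only, Cohort 1b is split at the injection into separate primary safety displays, and no rule covers an event that spans the injection. Where the worsening stays on the original record, its post-dose grade or seriousness is shown as pre-dose. Where a new record is opened, it is counted as in Cohort 1a. The result depends on a data-entry choice that the documents leave open, and the conflict between protocol 6.2.1 and protocol 9.4.3 with SAP 5 makes uneven entry more likely.

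The number of affected participants cannot be estimated and may be zero. For each one, the error is 1/n in the direction of a lower post-dose rate, on the assumed n above. It is worth correcting because the remedy is a sentence or two in the SAP.

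**What to change.** 1. In SAP 8.1.1, define a post-vaccination TEAE for Cohorts 1a and 1b as an event that starts, increases in grade, or becomes serious on or after the ARCT-021-02 injection. Assign the window by the date of that change.
2. Choose one recording rule: either a new linked record dated at the change, or a change date on the existing record. To avoid double counting, show the pre-injection grade only in the Pre-Study display and the post-injection grade only in the post-vaccination display.
3. Reconcile protocol 6.2.1 with protocol 9.4.3 and SAP 5 on how between-study events in Cohort 1b are entered.
4. SAP 5.1 bars changes to the interim SAP once data are pulled. If that has happened, apply the rule in the final SAP.

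The cost is SAP wording, a note on eCRF completion, and a few date queries for Cohort 1b events ongoing at Day 1. The post-dose rate may come out slightly higher.
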